#### Date Range:

Check all that apply (data includes medical records, images, specimens).

(5a) Only data that exists before the IRB submission date will be collected.

(5b) The study involves data that exist at the time of IRB submission **and** data that will be generated after IRB submission. Include this activity in the Methods section.

#### Examples

- The study plans to conduct a retrospective chart review and ask subjects to complete a questionnaire.
- The study plans to include subjects previously diagnosed with a specific disease and add newly diagnosed subjects in the future.

(5c) The study will use data that have been collected under another IRB protocol. Include in the Methods section and enter the IRB number from which the research material will be obtained. *When appropriate, note when subjects have provided consent for future use of their data and/or specimens as described in this protocol.*

Enter one IRB number per line, add more lines as needed

Data    Specimens    Data & Specimens \_\_\_\_\_

Data    Specimens    Data & Specimens \_\_\_\_\_

Data    Specimens    Data & Specimens \_\_\_\_\_

(5d) This study will obtain data generated from other sources. Examples may include receiving data from participating sites or an external collaborator, accessing an external database or registry, etc. Explain the source and how the data will be used in the Methods section.

(6) Video audio recording: *Describe the plan to maintain subject privacy and data confidentiality, transcription, store or destroy, etc.*

## HIPAA Identifiers and Protected Health Information (PHI)

Protected health information is medical data that can be linked to the subject directly or through a combination of indirect identifiers.

Recording identifiers (including a code) during the conduct of the study allows you to return to the medical record or data source to delete duplicate subjects, check a missing or questionable entry, add new data points, etc. De-identified data is medical information that has been stripped of all HIPAA identifiers so that it cannot be linked back to the subject. De-identified data is **rarely** used in the conduct of a research study involving a chart review.

**Review the list of subject identifiers below and, if applicable, check the box next to each HIPAA identifier being recorded at the time of data collection or abstraction.** Identifiers apply to any subject enrolled in the study including Mayo Clinic staff, patients and their relatives and household members.

**Internal** refers to the subject's identifier that will be recorded at Mayo Clinic by the study staff.

**External** refers to the subject's identifier that will be shared outside of Mayo Clinic.

Check all that apply:	INTERNAL	EXTERNAL
Name		
Mayo Clinic medical record or patient registration number, lab accession, specimen or radiologic image number	X	
Subject ID, subject code or any other person-specific unique identifying number, characteristic or code that can link the subject to their medical data	X	
Dates: All elements of dates [month, day, and year] directly related to an individual, their birth date, date of death, date of diagnosis, etc.	X	
Note: Recording a year only is not a unique identifier.		
Social Security number		
Medical device identifiers and serial numbers		
Biometric identifiers, including finger and voice prints, full face photographic images and any comparable images		
Web Universal Resource Locators (URLs), Internet Protocol (IP) address numbers, email address		
Street address, city, county, precinct, zip code, and their equivalent geocodes		
Phone or fax numbers		
Account, member, certificate or professional license numbers, health beneficiary numbers		
Vehicle identifiers and serial numbers, including license plate numbers		
Check 'None' when none of the identifiers listed above will be recorded, maintained, or shared during the conduct of this study. (exempt category 4)	 None	 None

## Data Analysis

*Power analyses may not be appropriate if this is a feasibility or pilot study, but end-point analysis plans are always appropriate even if only exploratory. Provide all information requested below, or provide justification if not including all of the information.*

### Power Statement:

Power simulations were based on anticipated analysis of group differences via *t*-tests, Chi-square tests, and Wilcoxon rank-sum tests. These simulations suggested that enrollment of 250 total patients (125 each in control/placebo group and lidocaine jelly treatment group) would allow us to detect a moderate effect ( $d = .5$ ,  $w = .3$ , and  $d=.5$  respectively) of differences between groups at a significance level of  $p < .05$  with power of 90% or greater in our planned analyses.

**Data Analysis Plan:** Primary analyses of interest are descriptive statistics for measures of pain, anxiety, biometric indicators (e.g., heart rate, blood pressure), and amount of total lidocaine administered by injection for each group. Secondary analyses will include statistical tests (e.g., *t*-tests,  $\chi^2$ , and Wilcoxon rank-sum) for comparison between control and treatment group for differences on pain, anxiety, and vital signs. Additional analysis of differences in pain/anxiety across repeated rounds of testing within groups will be explored given sufficient data via descriptive statistics, statistical test, and possible mixed models comparing changes over repeated rounds between groups (dependent on rates of patients with multiple-stage Mohs procedures).

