## Study Design and Methods

### Methods:

We will conduct a prospective, randomized trial of 250 patients receiving Mohs micrographic surgery to lesions on the nose. Annually Mohs micrographic surgery is performed on approximately 900 patients with 30% of these procedures being performed on lesions on the nose. Patients receiving Mohs treatment for lesions on the nose will be randomly assigned to one of two groups: (1) those whose wounds will be dressed with lidocaine jelly (treatment group), and (2) those whose wounds will be dressed with surgical lubricant (control/placebo group).

All patients will receive a pre-treatment baseline pain/anxiety survey followed by an initial lidocaine injection. The amount of lidocaine/epinephrine injection each patient receives throughout remaining stages of surgery will be recorded, as per the current workflow. All patients will complete a second pain/anxiety survey immediately after numbing but prior to the first stage of surgery.

After the first stage of surgery, either lidocaine jelly or surgical lubricant will be applied to the wound followed by a pressure bandage as per standard practice. Dressing are removed immediately prior to the next stage of surgery. After each subsequent stage of surgery, an identical wound dressing will be placed on the operative site.

Immediately prior to each subsequent stage of surgery, we will assess patients' pain sensation, and additional lidocaine/epinephrine will be injected if needed. After the surgical site is re-anesthetized, vital signs will be recorded and the Pain/Anxiety survey administered immediately prior to the first incision of that stage.

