### Endpoints

**Primary:** patient pain/anxiety score as indicated by survey, and quantity of Lidocaine Hydrochloride (Xylocaine) Injection with Epinephrine

**Secondary:** Blood pressure and heart rate, any history of Mohs surgery (any location, any provider)

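### The between-arm pain and anxiety tests leave out the baseline score collected on every patient, and prior Mohs history is listed as an endpoint

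*Combined protocol and SAP*

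**What the plan says.** **Measurements (Study Design and Methods, Methods).** Two surveys come before the randomised dressing:

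- "All patients will receive a pre-treatment baseline pain/anxiety survey followed by an initial lidocaine injection".
- "All patients will complete a second pain/anxiety survey immediately after numbing but prior to the first stage of surgery".

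The randomised material first reaches the patient later: "After the first stage of surgery, either lidocaine jelly or surgical lubricant will be applied to the wound followed by a pressure bandage". At each subsequent stage the site is re-anaesthetised and vital signs are recorded, with "the Pain/Anxiety survey administered immediately prior to the first incision of that stage".

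**Analysis (Data Analysis, Data Analysis Plan).** Descriptive statistics are called primary. The secondary analyses are statistical tests, with t, chi-square and Wilcoxon rank-sum given as examples, "for comparison between control and treatment group for differences on pain, anxiety, and vital signs". No covariate, ANCOVA or change score is named. Beyond this the plan offers exploratory work, including "possible mixed models comparing changes over repeated rounds between groups (dependent on rates of patients with multiple-stage Mohs procedures".

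**Endpoints.** The pain/anxiety score is a primary endpoint. The secondary endpoints are "Blood pressure and heart rate, any history of Mohs surgery (any location, any provider".

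**The concern.** A score on the same instrument, taken from every patient before any treatment, is usually the first covariate to consider for a later score. Randomisation makes the comparison fair without it, but between-patient variation that the baseline could explain stays in the error term. Confidence intervals are then wider than the collected data require.

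The plan's only possible route to using the early surveys is a model that may or may not be fitted, depending on how many patients have several stages, and that names no baseline term. If adjustment is not fixed beforehand, choosing between adjusted and unadjusted results after seeing the data would be open to question.

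The loss would matter if the true effect is smaller than d = 0.5, or if fewer than 250 patients supply a score after the dressing.

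Prior Mohs history is a separate and smaller matter. It is fixed before randomisation, so it describes the patient and cannot be an outcome of the dressing. The plan gives it no role as covariate, stratification factor or subgroup, and plans no between-arm test of it.

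**Working it through.** **Inputs from the Power Statement.** "enrollment of 250 total patients (125 each in control/placebo group and lidocaine jelly treatment group"; d = 0.5 for the t-test and Wilcoxon, w = 0.3 for chi-square; p < .05; power of at least 90%. Sidedness is not stated, so two-sided is assumed.

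**Input that is assumed.** rho, the correlation of the covariates with the first post-dressing score. It is not in the documents and may differ between pain and anxiety. Range used: 0, 0.3, 0.5, 0.7.

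**Step 1: the plan's own figure.**

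- t-test: noncentrality = d × √(n/2) = 0.5 × √(125/2) = 3.95 on 248 df, which gives power 97.6%.
- Chi-square: noncentrality = 250 × 0.3² = 22.5, which gives 99.7% at 1 df and 97.3% at 5 df.
- Wilcoxon: 97.1% using relative efficiency 3/π, and 96.9% in 5,000 simulated trials.

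The claim of 90% or more is reproduced if all 250 patients contribute. About 85 per arm would give 90% for the t-test.

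**Step 2: the effect of adjustment.** ANCOVA leaves residual variance (1 − rho²), in units of the outcome variance. Hence:

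- noncentrality = [d / √(1 − rho²)] × √(n/2)
- 95% CI half-width = 1.97 × √[2(1 − rho²)/125], in SD units
- unadjusted total N giving the same precision = 250 / (1 − rho²)

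Example, rho = 0.5 and d = 0.3: (0.3 / 0.866) × √62.5 = 2.74, power 78%. Without adjustment: 0.3 × √62.5 = 2.37, power 66%.

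| Assumed rho | 0 | 0.3 | 0.5 | 0.7 |
|---|---|---|---|---|
| Fall in residual variance | 0% | 9% | 25% | 49% |
| d detectable with 90% power | 0.41 | 0.39 | 0.36 | 0.29 |
| Power at d = 0.3 | 66% | 70% | 78% | 91% |
| Power at d = 0.5 | 97.6% | 98.5% | 99.5% | >99.9% |
| 95% CI half-width (SD) | 0.25 | 0.24 | 0.22 | 0.18 |
| Equivalent unadjusted N | 250 | 275 | 333 | 490 |

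With two covariates (246 df, rho read as the multiple correlation), power at d = 0.3 is unchanged to three decimals: 0.656, 0.697, 0.779, 0.911. A simulation of 8,000 trials per rho with one covariate agrees: ANCOVA power 0.653, 0.706, 0.778, 0.909, against 0.655 to 0.663 for the t-test.

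**Step 3: fewer patients with a post-dressing score.** Background sends patients with negative margins to reconstruction, and Methods does not say whether reconstruction counts as a stage. Some patients may therefore have no survey after the dressing. The share who do is not given; 50% and 30% are assumed. The same formula is used with n = 62.5 and 37.5 per arm, at d = 0.5:

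| Assumed rho | 0 | 0.3 | 0.5 | 0.7 |
|---|---|---|---|---|
| 50% contribute | 79% | 83% | 89% | 97% |
| 30% contribute | 57% | 61% | 69% | 85% |

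**The case against.** The strongest reply is that nothing planned is wrong. The tests are valid, the stated power is met with room to spare at d = 0.5, and d = 0.3 is not an effect size the protocol names. The larger gains also need a high rho. For pain that is doubtful: the baseline precedes any injection, while later scores follow surgery and re-anaesthesia. All of this stands. It makes the point one of efficiency and means the gain could be close to nil.

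A second reply is that the plan leaves room for adjustment: the tests are only examples, and the mixed model could take in the early surveys. That is possible, but neither passage commits to it. Prespecification is what gives an adjusted result its standing.

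A third reply is that if many patients have no post-dressing survey, the undefined time-point and analysis population matter more than the covariate. That is fair. Baseline adjustment does not cure this; it only recovers part of the lost precision among those who contribute.

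A fourth is that nothing in the documents shows prior Mohs history to be prognostic. That is also true, and the case for adjustment rests on the baseline score. One further covariate costs almost nothing at this sample size.

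**Conclusion.** The concern holds. The between-arm pain and anxiety comparisons name no baseline term although a baseline is planned for every patient, and no other passage commits to using it. This is avoidable imprecision on a primary endpoint; it is neither bias nor a failure of the stated power.

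With all 250 patients, adjustment adds at most about 2 points of power at d = 0.5. At d = 0.3 it adds between nothing (rho = 0) and about 25 points (rho = 0.7). Under the assumption that half the patients contribute, the unadjusted test falls to 79% at d = 0.5 and misses the plan's 90%; adjustment brings it to 89% at rho = 0.5. All gains rest on the assumed rho and, in the last case, on the assumed share contributing. The change should be made because it is nearly free, but the trial does not fail without it.

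Listing prior Mohs history as an endpoint is a labelling error with no effect on any planned test.

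**What to change.** **Data Analysis Plan**

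- Make the between-arm comparison of pain, and separately of anxiety, an ANCOVA of the first post-dressing score on arm, adjusting for the pre-treatment score of the same measure and prior Mohs history (yes/no).
- State which patients have a first post-dressing score and so enter this analysis.
- Name one alternative for strongly skewed scores (rank-based ANCOVA or proportional odds), with the criterion for using it set before the data are seen.
- Add the post-numbing score as a covariate only if it is collected before patient and staff know the allocation. The documents do not say when allocation occurs.
- Keep the unadjusted tests as supporting analyses and the mixed model for later rounds.

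**Endpoints**

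- Move prior Mohs history from the secondary endpoints to baseline characteristics and covariates.

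**Cost.** Plan wording only. The baseline survey and prior Mohs history are already to be collected, so no extra patients, visits or measurements are needed. If rho is near zero, the loss is two of 248 degrees of freedom.

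### The pain/anxiety endpoint has no time point, and the repeated-rounds analysis does not separate surveys taken before the dressing from those taken after it

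*Combined protocol and SAP*

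**What the plan says.** The Endpoints section lists "patient pain/anxiety score as indicated by survey" as primary, with no survey or time point named.

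The Methods section fixes the sequence. A baseline survey comes before the initial injection. Then "All patients will complete a second pain/anxiety survey immediately after numbing but prior to the first stage of surgery". Jelly or lubricant is first applied after that stage and again after each later one. Before each later stage sensation is checked, more anesthetic is injected where needed, and only then, once the site is numb again, is the survey given.

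The Background section says that more tissue is removed only when margins are positive; otherwise the wound is reconstructed.

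The Data Analysis Plan (under Power Statement) makes descriptive statistics primary and two-group tests secondary. It adds "Additional analysis of differences in pain/anxiety across repeated rounds of testing within groups", to be explored if data suffice, and "possible mixed models comparing changes over repeated rounds between groups", depending on how many patients have several stages. It does not say which rounds enter, which is the baseline, or how top-ups and the changing patient set are handled.

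**The concern.** Two of the surveys cannot reflect the randomized dressing, because they are taken before it is applied. The later ones can, but each follows a need-based injection whose use is itself an outcome of the dressing. The plan treats all of them as rounds of one series.

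Three consequences follow.

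- The two-group tests need one value per patient, and the choice of survey is left open until the data are in.
- A within-group change from round to round is not a comparison of randomized groups. It carries the initial injection, habituation and the change in who is still being measured.
- A group-by-round trend can be read as the jelly gaining or losing efficacy when it partly reflects top-ups.

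At stake is whether an effective dressing could be reported as having little effect on pain/anxiety, or as wearing off.

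**Working it through.** **1. The plan's own figure.** Inputs from the Power Statement: 125 per arm, d = 0.5 (t-test and rank-sum), w = 0.3 (chi-square), alpha 0.05 (two-sided assumed). The noncentrality for the t-test is 0.5 x sqrt(125/2) = 3.95, giving 97.6% power. Chi-square gives 99.7% (1 df) to 98.0% (4 df). Rank-sum gives 97.0% under normality and 95.5% in the worst case. The claim of "with power of 90% or greater in our planned analyses" is reproduced for two-group tests with one value per patient. No repeated-measures model was powered.

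**2. Dilution if pre-dressing surveys count as outcome.** A patient with one return has three surveys, one of them after the dressing.

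- Effect on the mean of three: 0.5 / 3 = 0.17 SD.
- SD of that mean with within-patient correlation r: sqrt((1 + 2r)/3), which is 0.73 at r = 0.3 and 0.89 at r = 0.7 (assumed range).
- Standardized effect: 0.167/0.73 = 0.23, or 0.167/0.89 = 0.19. Power with 125 per arm: about 44% and 31%.

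If only multi-stage patients have a post-dressing survey, the loss is greater. A random-intercept simulation (SD 1, intraclass correlation 0.5, true effect 0.5 SD at each of up to three post-dressing rounds) gave:

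| Multi-stage share (assumed) | Group effect over all rounds: estimate, power | Post-dressing rounds with pre-dressing baseline: estimate, power |
|---|---|---|
| 30% | -0.07, 9% | -0.51, 83% |
| 40% | -0.09, 13% | -0.50, 93% |
| 50% | -0.12, 22% | -0.50, 98% |

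**3. Attenuation from need-based top-ups.** Assume a pre-injection score that is 0.5 SD lower with jelly, and a top-up of fixed size given above a threshold. Then

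survey difference = -0.5 + top-up size x (share topped up in control - share topped up with jelly).

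| Threshold (SD) | Topped up: control, jelly | 1 SD top-up | 1.5 SD top-up |
|---|---|---|---|
| -0.5 | 69%, 50% | -0.31 | -0.21 |
| 0 | 50%, 31% | -0.31 | -0.21 |
| 0.5 | 31%, 16% | -0.35 | -0.27 |

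This happens at the first return. If 30% to 60% of each top-up persists to the next return, then at thresholds -0.5 and 0 the survey difference falls over three post-dressing rounds from 0.31 to 0.19-0.27 (1 SD top-up) or from 0.21 to 0.11-0.18 (1.5 SD), with the jelly's own effect held constant. If nothing persists, there is no further fall.

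**4. Changing patient set.** Suppose lesion extent correlates 0.3 or 0.5 with pain, and only margin-positive patients continue. From the first to the third post-dressing round the jelly arm's mean drifts from -0.29 to -0.13 (correlation 0.3) or from -0.16 to +0.10 (correlation 0.5). The between-arm difference stays at -0.50 throughout.

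**5. Size of the first post-dressing contrast.** If the reconstruction return is not a stage in the Methods sense, only multi-stage patients have this survey. Patients per arm = 125 x share; unadjusted t-test at d = 0.5:

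| Multi-stage share (assumed) | Per arm | Power |
|---|---|---|
| 20% | 25 | 41% |
| 30% | 37.5 | 57% |
| 40% | 50 | 70% |
| 50% | 62.5 | 79% |

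These powers do not include the attenuation in step 3.

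**The case against.** The strongest reply is that the quoted analysis is the lowest tier of the plan: additional, exploratory and conditional on data. The primary analyses are descriptive, the secondary ones are two-group tests, and their stated power reproduces. Nowhere does the plan average scores over all rounds, and in a model of change the pre-dressing surveys are a natural baseline. All of this stands. It limits the weight of the point but does not remove it: within-group tests are still planned, the baseline role is not stated, and the missing time point belongs to a primary endpoint.

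Four stronger readings are tempting, and the documents do not support them.

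- *The first return compares the arms at equal injection history.* That is true on arrival only. The survey follows the top-up, so this contrast is attenuated too.
- *A group-by-round trend would necessarily show fading.* One could assume that 90% of control and 40% of jelly patients need a top-up one wait after injection, and that p of jelly patients need one after two waits. The second-return gap is then 0.90 - (0.6p + 0.4 x 0.40): 20 points at p = 90%, 29 at 75%, 38 at 60%, and 50 (no fading from the first return's 50) at 40%. The answer depends on p, which the documents do not give, and the plan does not analyse top-up need by round.
- *The shrinking subset biases the between-arm comparison.* First-stage margins precede the dressing, and jelly is not plausibly a cause of later ones. The subset costs power and distorts within-arm trends only.
- *Later returns are invalid.* Comparing arms there still estimates the effect of a policy of using jelly. How much emphasis to give it is partly preference.

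**Conclusion.** The point holds as a gap in the analysis plan with a concrete, inexpensive remedy. The primary pain/anxiety endpoint lacks a time point, and the within-group tests across rounds cannot isolate the dressing. These two statements rest on the documents alone.

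The sizes are conditional. The fall from 0.5 to 0.17 SD is arithmetic, but applies only if pre-dressing surveys are used as outcome and the patient has one return. The attenuation to 0.21-0.35 SD and any later shrinkage rest on assumed top-up thresholds, sizes and persistence. The 41% to 79% power rests on an assumed multi-stage share and on reconstruction not counting as a stage. If it does count, every patient who returns as planned has a post-dressing survey, and the subset problem starts one round later.

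Neither the stated two-group power at 125 per arm nor the analysis of total injected quantity is affected.

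**What to change.** Change the wording of the Data Analysis Plan and the Endpoints section:

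1. Name the between-arm comparison at the first post-dressing survey as the main pain/anxiety contrast. Adjust it for the pre-dressing surveys as baseline, and never count them as outcome.
2. Replace the within-group round-to-round tests with between-arm contrasts on post-dressing rounds, with round as a factor.
3. Report top-up use at that return, by arm, next to the score, because the survey follows the top-up.
4. Treat later returns as exploratory, report the number of patients per round by arm, and state that a group-by-round term will not be read as a change in jelly efficacy.
5. State whether the reconstruction return counts as a subsequent stage. If it does not, say that the main contrast covers multi-stage patients only, and restate its power with the expected multi-stage share.

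The cost is wording, with no added patients, visits or measurements. The downside is less emphasis on later-round data and, if reconstruction does not count, an open statement that the main pain/anxiety contrast has fewer patients than the 250 enrolled.
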